1.2. Secondary Objectives

Specific Aim 3: Mediation Analyses. Our tertiary aim is to examine and compare the mechanism of treatment changes in yoga and traditional CBT for GAD. We predict that treatment changes in responder rates during yoga treatment will be mediated via changes in mindfulness and changes in vagal tone (Hypothesis 3.1), whereas changes in CBT will be mediated via changes in maladaptive cognitions (Hypothesis 3.2.). Moderators of "responder rates" will also be examined.

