9. STATISTICAL CONSIDERATIONS

9.1 General Design Issues

The specific aims and hypotheses are as follows:

Specific Aim 1: Short-term Efficacy of Yoga: Our primary objective is to examine the short-term treatment efficacy of yoga on GAD symptoms. We expect that, at post-treatment, a significantly greater proportion of individuals randomized to receive yoga will be classified as "responders" to treatment (CGI-I ≤ 2) than for individuals who receive SE (Hypothesis 1.1). We further expect

that a greater proportion of individuals receiving CBT for GAD will be classified as "responders" than for those receiving SE (Hypothesis 1.2). Moreover, we predict that the rate of "responders" in individuals receiving yoga will be comparable to those receiving CBT at post-treatment (Hypothesis 1.3).

Specific Aim 2: Long-term Efficacy of Yoga (Exploratory Aim): Our secondary aim is to examine the long-term treatment efficacy of yoga on GAD symptoms. We hypothesize that yoga and CBT will be equally effective at the 6-month follow-up (i.e., the "responder" rate for yoga will not be inferior to that for CBT), and that yoga and CBT will each have higher "responder" rates than SE (Hypothesis 2.1-2.3).

Specific Aim 3: Mediation Analyses. Our tertiary aim is to examine and compare the mechanism of treatment changes in yoga and traditional CBT for GAD. We predict that treatment changes in responder rates during yoga treatment will be mediated via changes in mindfulness and changes in vagal tone (Hypothesis 3.1), whereas changes in CBT will be mediated via changes in maladaptive cognitions (Hypothesis 3.2.). Moderators of "responder rates" will also be examined.

These hypotheses can be tested in a five-year multi-site study to examine the comparative efficacy of yoga, CBT, and stress education, a previously employed control condition, for patients with GAD. Patients with GAD will receive 12-weekly yoga, CBT, or stress education sessions delivered in a group format controlling for attention, time, and group format. Independent evaluators will perform assessments before the 12-session intervention phase, at mid-treatment, after the intervention, and at 6-month follow-up.

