9.2 Sample Size and Randomization

A non-inferiority test is the most direct test of our hypothesis that Yoga will be as effective as CBT for both short-term and long-term outcomes. We will perform a non-inferiority test using response rate (response rate is defined as CGI-I ≤ 2) as the outcome on which to compare CBT and Yoga at posttreatment and at follow-up. Since some attrition may occur, we will use last observation carried forward to insure an intent-to-treat analysis. The non-inferiority margin will be half the difference in response rates between the active comparison (CBT) and placebo. Based on earlier literature, we can expect response rates in our particular CBT and placebo conditions of 57.9% in CBT and 22.2% in placebo. Thus, our non-inferiority margin will be set at ¹/₂ the difference between 56.7 and 22.2, or 17.85%. Using the power analysis program PASS 12, we find that the number of subjects required to obtain .80 power for the non-inferiority test comparing CBT and Yoga is 95 participants in each of the 2 conditions. We verified this number in a 1000 simulation Monte Carlo study using these same parameters. This number is higher than the number proposed in the original grant. Thus, we will increase the N per cell in CBT and Yoga to 95 (22 additional patients per site) to have adequate power for this non-inferiority test. While the original study was budgeted based on a lower number of participants, with careful management of costs we believe we can manage this increase in participants within the full study budget if awarded as proposed.

For the superiority tests (CBT vs. SE and Yoga vs. SE) on the secondary outcomes (which are continuous), we used the MRM power analysis program PinT 2.12. We assumed 25% missing data, and used data from our recent CBT trials (e.g., Stern et al., 2012) to estimate the variances and covariances needed for PinT. PinT indicated greater than .80 power to detect an effect size as small as d=.27, between a small (d=.20) and medium (d=.50) effect size.

We predict that changes in mindfulness will mediate changes in outcome over time for patients in the Yoga condition, and changes in cognitions will mediate changes in CBT. Plus, changes in RSA and cortisol may also mediate changes in outcome across conditions. We further predict that treatment condition will moderate the effect of Time on the mediators ("a" paths).

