This growth curve model will be used to test differences between treatment conditions for our primary outcome (response to treatment) and for CGI-S, since these outcomes are measured frequently enough (7 times during treatment) to accurately model the growth curve. However, the other secondary outcomes are measured at most3 times during treatment (baseline, week 6, post-treatment), with secondary sleep measures administered only twice (baseline and posttreatment), thus disallowing accurate assessment of their growth curve. Thus, these outcomes will use an MRM employing an ANOVA type design (see for example, Liu, Rovine, & Molenaar, 2012). In this kind of model, time is treated as a categorical variable (using2 dummy variables [one for each assessment except the baseline assessment] to code the 3 assessments). The three treatment conditions (Yoga, CBT, and SE) will be coded using the 2 dummy variable contrasts (Yoga vs. SE and CBT vs. SE). Interactions will be formed between each treatment condition contrast and each assessment dummy variable. This coding freely estimates the means for the outcome at each assessment, without any constraint from a specific growth curve. This design is similar to a 3 x 3 repeated measures ANOVA with the exception that it includes all patients that complete at least one assessment, the outcome can be dichotomous, the covariance structure of the repeated measures can take almost any form, and this approach assumes data are missing at random (MAR) or not missing completely at random (MCAR). The significance of the interaction between a treatment condition contrast (e.g., Yoga vs. SE) and an assessment dummy variable (e.g., for the post-treatment assessment) will test whether the change from baseline to that assessment is significantly different between the treatment conditions. Using this coding scheme, all contrasts between treatment conditions at all assessments are provided by this one analysis. Thus, this approach has the added benefit of having all contrasts between the treatment conditions at each assessment being conducted on the same sample.

Demographics and comorbid diagnoses will be used as covariates in all analyses and considered as possible moderators of outcome at each assessment. An additional moderator that will be investigated is homework adherence.

Planned Secondary Analysis of Sensitivity of Growth Curve Model for Primary Outcome

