allow us to assess the effect of CBT vs. SE and Yoga vs. SE separately for those who received additional treatment and those who did not. A further analysis will compare the rates at which subjects in the 3 conditions seek additional treatment during the FU period.

Secondary Mediation Analysis for Primary Outcome:

We are interested in mediation of our primary outcome: response at post-treatment. Thus, this analysis will include all assessments through and including post-treatment (but not FU). Our mediation analysis includes 2 independent variables (the contrast of Yoga vs. SE and the contrast of CBT vs. SE) and 3 mediators: mindfulness, vagal tone, and maladaptive cognitions. The "a" paths in the mediation analysis will be the effects of each of the 2 independent variables on each of the 3 mediators. These paths will be derived from three MRMs, one for each mediator as the dependent variable. These MRMs will be identical to the models described above with Time centered at post-treatment. Thus, the effect of each contrast (Yoga vs. SE and CBT vs. SE) will be their effect on each mediator at post-treatment. The "b" paths will be derived from the GLMM model (described above) for differences between treatment conditions at post-treatment, with the dependent variable being "response". The 3 mediators will be included in this growth curve model as additional simultaneous predictors of response. The regression coefficients for the mediators in this analysis become the "b" paths in the mediation analysis (the paths from each mediator to outcome). Significance of mediated pathways will be determined using biascorrected bootstrap mediation analysis (e.g., Fritz and MacKinnon, 2007 [137]). We predict that changes in mindfulness will mediate changes in outcome over time for patients in the Yoga condition, and changes in cognitions will mediate changes in CBT. Plus, changes in RSA and cortisol may also mediate changes in outcome across conditions.

Missing Data. Although we will make every effort to reduce missingness, it is inevitable that some data will be missing. We will use pattern mixture modeling (Hedeker & Gibbons, 2006; Enders, 2011 [138-139]) and rerun our analyses coding for various missing data patterns (no missing data, early dropouts, late dropouts, FU dropouts, etc.) to determine both if missingness impacts our findings and how the differences between treatment conditions depend on the missing data pattern.

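### The mediator-to-response ('b') path in section 9.6 omits the mediators' baseline values, so a mediator that treatment moves can be declared a mediator even if its change does not affect response

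*Combined protocol and SAP*

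**What the plan says.** Sections 1.2 and 9.1 state Aim 3 in terms of change. Response under yoga is expected to be "mediated via changes in mindfulness and changes in vagal tone", and response under CBT to be mediated by change in maladaptive cognitions.

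The mediation part of section 9.6 builds the test in three pieces.

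- **'a' paths.** There is one MRM per mediator, using all assessments up to post-treatment, with time centred there: "Thus, the effect of each contrast (Yoga vs. SE and CBT vs. SE) will be their effect on each mediator at post-treatment".
- **'b' paths.** These come from the response GLMM: "The 3 mediators will be included in this growth curve model as additional simultaneous predictors of response".
- **Test.** "Significance of mediated pathways will be determined using biascorrected bootstrap mediation analysis".

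The general covariate rule in section 9.6 is: "Demographics and comorbid diagnoses will be used as covariates in all analyses". Baseline mediator values are not on that list and are not added in the mediation part. Elsewhere in section 9.6, the logistic sensitivity analysis does adjust for baseline CGI-S and SIGH-A.

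The schedule in section 6.1 collects FFMQ, MCQ and RSA at baseline, week 6, post-treatment and follow-up. Its footnote says the CGI-I is not given at screening or baseline.

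Section 9.2 describes the 'a' paths in other terms: "treatment condition will moderate the effect of Time on the mediators". Its power study assumes large 'a' paths and a medium 'b' without giving numbers, and reports power above .81.

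**The concern.** A mediator's value after baseline has two parts: where the patient started and how far the patient moved. Hypotheses 3.1 and 3.2 concern the second part. A 'b' coefficient on the unadjusted value mixes both. If patients who start out more mindful respond more often for any reason, 'b' is non-zero even when movement in mindfulness has no effect. Section 6.2 itself presents the FFMQ as a trait measure.

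Randomization protects the comparison of arms on the mediator. It does not protect the association between mediator and response. The GLMM's random intercept does not help either, because it is assumed independent of the predictors. The bootstrap gives an interval for a×b but cannot remove confounding from 'b'.

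At stake are the trial's mechanistic claims. A spurious 'b' multiplied by a real 'a' would be reported as a mediated pathway.

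**Working it through.** **Inputs from the documents.** Arms of 95, 95 and 40; expected response 57.9% (CBT) and 22.2% (placebo); bias-corrected bootstrap.

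**Assumptions, because the documents give none.** Two-sided 95% interval; treatment effect on the mediator a = 0.3 to 0.8 SD; baseline-to-post correlation ρ = 0.3 to 0.7; baseline log odds ratio γ per SD.

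**Model.** Baseline mediator M0 has SD 1. Post-treatment M12 = ρ·M0 + a·arm + error, with within-arm variance 1. The log odds of response depend on arm and γ·M0, with coefficient **zero** on M12. 'a' is the arm contrast on M12. 'b' comes from a logistic regression of response on two arm dummies and three post-treatment mediators. This simplifies the three-level GLMM to one time point, without clustering or missing data. Simulated response was 54% in the active arms and 20–21% in SE. Monte Carlo error is up to about 2 points.

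**1. The plan's power figure.** With mediation real and a = 0.8, power is 0.70 at b = 0.35 (log odds ratio per SD), 0.80–0.81 at 0.40 and 0.92–0.93 at 0.50. The stated figure is plausible. It cannot be reproduced exactly, since large and medium carry no numbers.

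**2. What 'b' picks up when change does nothing.** Within an arm, the slope of M0 on M12 is ρ, so b ≈ ργ. With γ = 0.707 (odds ratio e^0.707 ≈ 2.03):

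- ρ = 0.3: 0.3 × 0.707 = 0.21 (simulated 0.18)
- ρ = 0.5: 0.5 × 0.707 = 0.35 (simulated 0.31)
- ρ = 0.7: 0.7 × 0.707 = 0.49 (simulated 0.46)

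The simulated values are slightly lower because logistic coefficients shrink when part of a predictor is left out. The last two lie close to the b of about 0.40 that gives the plan's own power.

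**3. False pathways at γ = 0.707, mediators unadjusted.**

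| a (SD) | ρ = 0.3 | ρ = 0.5 | ρ = 0.7 |
|---|---|---|---|
| 0.3 | 11–12% | 23–25% | 35–37% |
| 0.5 | 21–22% | 47% | 69–70% |
| 0.8 | 26–27% | 58–60% | 86–89% |

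A second simulation at a = 0.8, using a joint test of 'a' and 'b' over odds ratios 1.5 to 2.0, gave 13–28%, 30–63% and 50–89% at the three correlations.

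**4. When treatment does not move the mediator (a = 0).** False pathways occur in 3–6.5% of trials for ρ = 0.5 to 0.9 and γ = 0.707 to 0.907.

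**5. Adding the baseline mediator.** The rates in step 3 fall to 5–7% at a = 0.5 to 0.8 and 2–5% at a = 0.3. In the second simulation they fall to about 5%, and adjusting 'b' alone did as well as adjusting both paths. At reliability 0.8 (a = 0.8), 9–13% remains.

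**6. Using change scores instead.** The within-arm slope of M0 on M12 − M0 is (ρ − 1)/(2 − 2ρ) = −1/2, so b ≈ −0.5 × 0.707 = −0.35 (simulated −0.32 to −0.33). False pathways occur in 20–74% of trials, now with a negative sign.

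**7. Closer to the planned model.** A random-intercept logistic GLMM with mediators at weeks 6 and 12 gave 35% and 59% at odds ratios 1.5 and 2.0, and 5% and 3% with baseline added. With a latent trait measured with error, rates were 40% and 85% unadjusted, 13% and 33% with the baseline value, and 6% and 3% with person-mean-centred mediators.

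**The case against.** **The 'b' model is underspecified rather than plainly wrong.** Section 9.6 does not say whether mediators enter as time-varying or post-treatment values, and they are measured less often than response. That is so, but neither reading includes a baseline term, and both show the problem (steps 3 and 7). Nor does it help to code everyone a non-responder at week 0 and enter the baseline mediator as a row. In simulation that gave 33% and 63% (ρ = 0.5) and 50% and 87% (ρ = 0.7) at odds ratios 1.5 and 2.0, against 5–7% with baseline as a covariate.

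**A reader might infer that any stable trait predicting response will be declared a mediator.** The documents do not support this. The test is on a×b, and randomization makes 'a' zero in expectation for a trait that treatment leaves alone (step 4). The error needs a real treatment effect on the mediator. The plan's power study does assume one, and a large one.

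**A reader might also infer that the 'a' path is biased because it compares levels.** It is not. Baseline is already a repeated measure in those MRMs, and under randomization the post-treatment contrast and the contrast in change have the same expectation.

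**The direction is unknown.** The CGI-I rates improvement, so patients who start lower may have more room to respond. 'b' would then be biased downward and real mediation masked. This stands, as does the point that correlations, odds ratios and reliability are all assumed.

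**Conclusion.** The defect is in the 'b' path. It takes mediator values without their baseline, so it is confounded by stable between-person differences, while Aim 3 is about change. For a mediator that treatment moves, the plan can declare mediation that is absent, or miss mediation that is present if the trait effect has the opposite sign.

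Over the ranges tried, the false-pathway rate runs from about 11% to 89% against a nominal 5%, and is lower for smaller 'a' and weaker baseline-to-post correlation. The existence of the confounding follows from the model as written. Its size and sign rest on quantities the documents do not give.

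Priority is low to moderate. Aim 3 is tertiary, and the efficacy and non-inferiority conclusions do not use this analysis.

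**What to change.** In the mediation part of section 9.6:

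- Add the baseline values of FFMQ, MCQ and RSA as covariates in the 'b'-path GLMM, beside the post-baseline mediator values. State how the post-baseline values enter.
- Do not replace levels by change scores alone (step 6).
- Leave the 'a'-path MRMs as they are. Baseline is an outcome row there, and adding it as a covariate would put it on both sides of the model.
- Reconcile sections 9.2 and 9.6 on whether the 'a' path is a treatment-by-time effect or a post-treatment contrast.
- Add a sensitivity analysis that splits each mediator into person mean and deviation and uses the within-person coefficient as 'b', because measurement error in the baseline leaves some confounding. It will rest on only two visits, weeks 6 and 12, with both a mediator value and a CGI-I rating.

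No new data are needed. The cost is a modest loss of power when mediation is real. In simulation with baseline added to both paths, power fell from 83% to 75% at a 'b' odds ratio of 1.6 and from 97% to 92% at 2.0, with no loss at 2.5. The stated power above .81 should be re-run with the adjusted model and with the assumed effect sizes given as numbers.

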Yoga for generalized anxiety disorder: A comparison between yoga, cognitive behavioral therapy, and stress education training

Objectives

The general purpose of the study is to determine whether yoga is an effective method for treating GAD, and its relative efficacy compared to a standard psychosocial intervention. Our primary objective is to examine the short-term treatment efficacy of yoga on GAD symptoms. Our secondary objective is to examine the long-term treatment efficacy of yoga on GAD symptoms. Our tertiary objective is to examine and compare the mechanism of treatment changes in yoga and traditional CBT for GAD.

Design and Outcomes

This five-year multi-site study will examine the comparative efficacy of yoga, CBT, and stress education, a previously employed control condition, for patients with GAD. Across 2 enrolling centers (BU and MGH) we will randomize 230 patients with GAD to one of three 12 session weekly study treatments: 12-weekly yoga (n=95), CBT (n=95), or stress education (SE: n=40). Independent clinical assessments will occur before the 12-session intervention phase, at mid-treatment, after the intervention, and at 6-month follow-up. All clinician-rated outcomes will be assessed by trained Independent Evaluators (IEs) blind to treatment assignment. Response (CGI-I of 1 or 2) will serve as the primary outcome measure alongside the SIGH A as the core secondary continuous measure. Secondary outcome measures also include the STAI, PSS, BDI-II and BAI, QOL, ISI, PSQI and PSWQ. The FFMQ, MCQ, pre-ejection period, and cortisol are examined as possible mediators of change. The Credibility/Expectancy Questionnaire will be administered to examine whether credibility and expectancy moderates therapy outcome. In addition, we will explore whether clinical characteristics (comorbid diagnoses) and demographic characteristics (age, sex, SES) are possible moderators. We hypothesize that Yoga and CBT will each be superior to SE at post-treatment FU, and Yoga and CBT will not differ based on equivalency analyses. We predict that treatment changes during yoga are mediated via changes in mindfulness and changes in vagal tone, whereas changes in CBT are mediated via changes in maladaptive cognitions.

Interventions and Duration

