diagnostic assessment. We conservatively estimate that 20% of eligible participants will discontinue the intervention prematurely, but all participants who are randomized will be included in the analysis with an intent to treat analytic approach. For ethical reasons, additional treatment will not be withheld for non responders (defined as CGI-I > 2) or anyone for whom additional intervention is indicated in any intervention condition during the 6 month follow up. Non responders (CGI-I>2) at week 12 will be assisted in finding appropriate care from our existing referral resources. All participants will receive 6 month assessments, but any additional treatment received by non responders will be adjusted for in the analyses.

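### Arm differences by dropout pattern cannot be usefully estimated against an SE arm of 40, so they are a weak basis for judging whether missing data affect week-12 response

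*Combined protocol and SAP*

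**What the plan says.** The Missing Data paragraph of section 9.6 plans pattern-mixture modelling, to "rerun our analyses coding for various missing data patterns (no missing data, early dropouts, late dropouts, FU dropouts, etc". It states two aims: to find out whether missingness affects the findings, and "how the differences between treatment conditions depend on the missing data pattern". It gives no cut-point between early and late dropout, minimum pattern size, merging rule, rule for averaging over patterns, or assumption that identifies unobserved week-12 response.

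The figures that determine pattern size are elsewhere:
- Design and Outcomes (Précis) gives the arm sizes: "12-weekly yoga (n=95), CBT (n=95") and "stress education (SE: n=40").
- Section 9.2 expects response rates of "57.9% in CBT and 22.2% in placebo".
- Section 3 says: "We conservatively estimate that 20% of eligible participants will discontinue the intervention prematurely".
- Section 9.2, in the power calculation for the continuous outcomes, says: "We assumed 25% missing data".

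Section 9.6 also plans two logistic regressions of post-treatment response, one with last observation carried forward (LOCF) and one in completers. Their stated purpose is to check sensitivity to the choice of growth curve. The Aim 1 model stops at post-treatment and leaves out the follow-up visit.

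**The concern.** Hypotheses 1.1 and 1.2 both compare an active treatment with SE, the smallest arm. The pattern-mixture rerun is the only planned analysis aimed at informative missingness. To show how arm differences depend on the pattern, it needs pattern-by-arm terms in a logistic mixed model that already carries a growth curve, a cohort level and covariates. Each such term against SE rests on the few SE patients in that pattern. Those who left before week 12 and have no week-12 rating also contribute no direct information on the quantity of interest. Their week-12 effect comes from extending a curve, itself chosen by AIC and BIC, beyond their last visit.

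The risk lies in interpretation. If the interaction is imprecise, it will usually be non-significant whether or not dropout is informative. A reassuring statement about missing data could then rest on a test with little chance of raising an alarm.

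**Working it through.** **Reference figure.** The documents give no patient count, power or precision for the pattern-mixture analysis. The related figure of 95 per arm (section 9.2) does reproduce. With 57.9% response in both arms, a margin of 0.1785, 80% power and one-sided alpha 0.05 (inferred, since alpha is not stated), n = (1.645 + 0.842)² × 2 × 0.579 × 0.421 / 0.1785² ≈ 95. One-sided 0.025 would give 121.

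**Inputs.** SE n = 40; yoga and CBT n = 95 each; response 0.579 in CBT and 0.222 in placebo; loss d = 0.20 (section 3) or 0.25 (section 9.2).

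**Assumptions, not in the documents.** SE responds at the placebo rate and yoga at the CBT rate. The loss applies equally in all arms and to week-12 ratings. It splits evenly between early and late. Response rates are the same in every pattern. Follow-up dropouts have week-12 data, so only the early and late patterns matter for Aim 1.

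**SE patients and responders**
- All SE dropouts: 40 × 0.20 = 8, or 40 × 0.25 = 10. Responders: 8 × 0.222 = 1.8, or 10 × 0.222 = 2.2.
- Each of two dropout patterns: 4 or 5 SE patients, with 0.9 or 1.1 responders.
- No-missing pattern: 32 or 30 SE patients, with 7.1 or 6.7 responders.
- Chance that a given dropout pattern has no SE responder: 0.778⁴ = 0.37, or 0.778⁵ = 0.29.

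**Precision of the active-versus-SE difference within one dropout pattern** (expected 0.579 − 0.222 = 0.357). Half-width = 1.96 × √[0.222 × 0.778 / n(SE) + 0.579 × 0.421 / n(active)].
- 20% loss, n = 4 and 9.5: 1.96 × √(0.0432 + 0.0257) = 0.51. On the odds-ratio scale the estimate is 4.8, with an approximate 95% interval of 0.33 to 71.
- 25% loss, n = 5 and 11.9: 1.96 × √(0.0345 + 0.0205) = 0.46.
- Completers, for comparison: 0.18 to 0.19.

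These half-widths treat week-12 response as known in every patient, which is optimistic.

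**Power of the interaction test.** Take a strongly informative case for yoga versus SE: 57.9% versus 22.2% in completers, and 22.2% in both arms among dropouts. Simulated with one binary outcome per patient, again taken as known, a likelihood-ratio test of pattern-by-arm detects this only about a quarter of the time.

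**Merging early and late.** SE then has 8-10 dropouts and 1.8-2.2 responders, and the half-width is 0.36 (20% loss) or 0.33 (25%). The dropout-specific contrast is still weak.

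**Averaging over patterns.** Completers carry 75-80% of the weight. If the effect in dropouts were zero, the average would be 0.80 × 0.357 = 0.29, or 0.75 × 0.357 = 0.27. The half-width of the average is about 0.16, with week-12 response again treated as known.

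**Yoga versus CBT.** With 9.5 or 11.9 patients per arm in each dropout pattern, the half-width is 0.44 or 0.40, against a margin of 0.1785.

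**The case against.** The strongest objection is that section 9.6 has two aims, and only the second needs precise pattern-specific contrasts. An effect averaged over patterns could meet the first, and the text does not rule out averaging or merging. This stands. A reader might infer that the analysis cannot show at all whether missing data change the primary result. The documents do not support that, because completers hold about seven SE responders and would dominate any averaged effect.

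Second, the loss rates are borrowed. The 20% is discontinuation of treatment, and section 8.1 encourages an endpoint assessment afterwards; the 25% was assumed for continuous outcomes. This also stands, but it does not rescue the by-pattern contrasts. If, for illustration, half of the 20% still attended week 12, 40 × 0.20 × 0.5 = 4 SE patients would remain over two patterns, or 2 × 0.222 = 0.4 responders in each. The cells shrink, although so does their influence.

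Third, the planned model uses repeated ratings, up to seven assessments per patient. The zero-responder chances above are therefore not probabilities that it fails to converge, and a reader should not take the point as a prediction of failure. The rerun also covers continuous outcomes, where empty responder cells do not arise.

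Fourth, LOCF and completer analyses are planned. They show whether the result survives two other treatments of missing outcomes, but neither varies the departure from missing-at-random by degrees.

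Finally, the plan nowhere says that a non-significant interaction will be read as no impact. That reading is a risk left open by the lack of a decision rule, not a stated intention.

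**Conclusion.** The point holds in a limited form. On the plan's figures, each of the early and late dropout patterns would contain about 4-5 SE patients and about one responder. Active-versus-SE differences within a dropout pattern would carry half-widths of about 0.46-0.51 and are not usefully estimable. Week-12 effects in dropouts without a week-12 rating are extrapolated under an assumption that the plan does not state. A null pattern-by-arm result would be weak evidence that missingness is harmless.

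This rests on the loss rates applying to week-12 ratings, on an even early/late split, and on common response rates across patterns. It does not extend to the no-missing pattern, to an effect averaged over patterns, or to follow-up dropouts. The yoga-versus-CBT comparison does not depend on SE numbers, though its by-pattern estimates are also too imprecise for the margin. The change is worth making before analysis: the primary analysis can stay as it is, but the conclusion about missing data needs a firmer basis.

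**What to change.** In the Missing Data paragraph of section 9.6:

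1. Label the by-pattern contrasts with SE as descriptive, and state that no conclusion about missingness will rest on the pattern-by-arm test.
2. Base the conclusion for week-12 response on delta-adjusted multiple imputation. Impute missing response under missing-at-random, then shift the odds of response among the missing outcomes separately by arm over a range fixed in advance. Report the tipping points at which the conclusions for Hypotheses 1.1, 1.2 and 1.3 change; the last is yoga-versus-CBT non-inferiority. No SE dropout cell has to be estimated, because the departure from missing-at-random is set by the analyst.
3. If a pattern-mixture estimate is kept, report the arm effect averaged over patterns instead of the interaction test. State the pattern definitions, the merging rule, the weights and the assumption that identifies week-12 response in dropouts. Merging early and late dropouts alone would not be enough.

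The cost is SAP wording and a small amount of extra analysis. The downside is less emphasis on the early/late split, which the SE arm is too small to support. The shift in odds cannot be learned from the data, so its plausible range needs clinical judgement and should be agreed before unblinding.
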